The changes made to the clinical study protocol MOR106-CL-204 Version 3.0, dated 15-Oct-2018, are listed below, reflecting a brief rationale of each change and the applicable sections.

Rationale: The wording regarding the prior use of biologics for AD has been updated to exclude only prior use of dupilumab. There is only one biologic currently approved for AD which is dupilumab. To avoid incurring any potential bias by including patients who have failed dupilumab treatment and are potentially treatment resistant, dupilumab will continue to be excluded. All other prior biologics will be considered as for prior non AD biologics, with a washout period of 5 half lives or 12 weeks.

Applicable Section: 4.5.2. Exclusion Criterion 4 (i and v)

Rationale: The wording has been updated in line with sponsors updated template text to allow subjects with a history of Hepatitis A and Hepatitis B to be included.

Applicable Section: 4.5.2. Exclusion Criterion 5

Version 4.0, final, 25-Jun-2019

Table 1:	Grading of AE Severity	60

LIST OF FIGURES

Figure 1: Schematic overview of the study design
--

LIST OF APPENDICES

Abbreviations

AD	atopic dermatitis
ADA	anti-drug antibody
ADL	activities of daily living
AE	adverse event
AESI	adverse event of special interest
ALT	alanine aminotransferase
API	active pharmaceutical ingredient
AUC_{τ}	area under the serum concentration-time curve for the dosing interval
AST	aspartate aminotransferase
BSA	body surface area
CD1	cluster of differentiation 1
C _{max}	maximum observed serum concentration
CSP	clinical study protocol
CSR	clinical study report
CRO	contract research organization
CRF	case report form
CTCAE	Common Terminology Criteria for Adverse Events
DNA	deoxyribonucleic acid
EASI	Eczema Area and Severity Index
EC ₅₀	50% effective concentration
ECG	electrocardiogram
ED	early discontinuation
ETD	early treatment discontinuation
EU	European Union
FIH	first-in-human
FSH	follicle stimulating hormone
GCP	Good Clinical Practice
GLP	Good Laboratory Practice

GGT	gamma glutamyl transferase
HBc	hepatitis B core
HBs	hepatitis B surface
HOME	Harmonising Outcome Measures in Eczema
HIV	human immunodeficiency virus
IB	investigator's brochure
ICF	informed consent form
ICH	International Council for Harmonisation of Technical Requirements for Pharmaceuticals for Human Use
IEC	Independent Ethical Committee
IGA	Investigators' Global Assessment
IgE	immunoglobulin E
IgG1	immunoglobulin G1
IL-17C	interleukin 17C
IL-17RE	interleukin 17 receptor E
IMP	investigational medicinal product
INR	international normalized ratio
IRB	Institutional Review Board
ISR	injection site reaction
iSRC	independent Safety Review Committee
IWRS	interactive web response system
LD	loading dose
LFT	liver function test
MAD	multiple ascending dose
NOAEL	no observed adverse effect level
NYHA	New York Heart Association
PD	pharmacodynamics
РК	pharmacokinetic
PUVA	psoralen and ultraviolet A
Q2W	once every 2 weeks
Q4W	once every 4 weeks

QTcB	QT interval corrected for the heart rate using Bazett's formula
QTcF	QT interval corrected for the heart rate using Fridericia's formula
RNA	ribonucleic acid
SAD	single ascending dose
SAE	serious adverse event
SAP	statistical analysis plan
SOC	System Organ Class
SUSAR	suspected unexpected serious adverse reaction
TARC	thymus and activation regulated chemokine
TBL	total bilirubin level
TCS	topical corticosteroid
TCI	topical calcineurin inhibitor
TEAE	treatment-emergent adverse event
Th2	type 2 T helper cell
TNF-α	tumor necrosis factor-alpha
ULN	upper limit of normal
UVB	ultraviolet B
VAS	visual analogue scale
WOCBP	women of childbearing potential

Definition of Terms

BMI	weight (kg) / (height $[m]$) ²
QTcB	$QTcB = QT / \sqrt{RR}$
QTcF	$QTcF = QT x (1000/RR)^{1/3}$

Objectives:

Primary Objective

 To investigate the safety and tolerability of repeated subcutaneous (s.c.) doses of MOR106 administered concomitantly with topical corticosteroids (TCS) in subjects with moderate to severe atopic dermatitis (AD) who are candidates for systemic therapy.

Secondary Objectives

- To evaluate the pharmacokinetics (PK) of repeated s.c. doses of MOR106 administered concomitantly with TCS.
- To monitor the occurrence of anti-drug antibodies (ADA) as a measure of immunogenicity after repeated s.c. doses of MOR106 administered concomitantly with TCS.

Other Objectives

Design:

This is a randomized, double-blind, placebo-controlled, multicenter Phase 2 study of repeated s.c. doses of 320 mg MOR106 or placebo, administered concomitantly with TCS. On Day 1 a loading dose (LD) will be administered (i.e. 2 x 320 mg MOR106, or placebo).

Adult subjects with moderate to severe AD who are candidates for systemic therapy will be randomized 2:1 to receive MOR106 or placebo every other week via s.c. injections (on Days 1, 15, 29, and 43). The 8-week treatment period, finishing on Day 57, is followed by a 16-week follow-up period, finishing on Day 169. A total of 60 subjects (n=40 on MOR106, and n=20 on placebo) will be enrolled in this study.

Version 4.0, final, 25-Jun-2019

Rationale:

This study is being conducted to obtain safety and preliminary efficacy information on the s.c. administration of MOR106 with concomitant TCS in subjects with moderate to severe AD who are candidates for systemic therapy in comparison to placebo with TCS.

TCS have been the primary treatment option for AD patients for many years and are commonly used as the first line of pharmacologic treatment in patients whose symptoms cannot be controlled with general measures such as allergen and irritant avoidance, skin hydration, and skin moisturization. TCS are also used to treat AD exacerbations. Therefore, many patients may use MOR106 in combination with TCS. For this reason, it is judicious to assess if MOR106 can be safely co-administered with TCS and to assess the added benefit. In order to standardize treatment conditions, the concomitant application of TCS and MOR106 or placebo starts on Day 1 for all subjects after a washout period for TCS of at least 7 days prior to the baseline visit (i.e. Day 1).

Endpoints:

Primary Endpoint

The incidence and severity of treatment-emergent adverse events (TEAEs), serious adverse events (SAEs), and adverse events of special interest (AESIs) through Day 169/ early discontinuation (ED) visit.

Secondary Endpoints

- MOR106 serum concentrations after repeated s.c. administrations from baseline through Day 169/ED visit.
- Occurrence of ADA from baseline through Day 169/ED visit.

Other Endpoints

MOR106-CL-204

Atopic Dermatitis (AD) is a chronic pruritic inflammatory skin disease that occurs most frequently in children, but also affects adults (Garmhausen, Hagemann, & Bieber, 2013). The main features of AD are the impairment of the skin barrier and dysfunction of the immune system accompanied with dry skin and severe pruritus that is associated with cutaneous hyperactivity to various environmental stimuli.

In AD the main goals of treatment are improving the appearance of the skin and relieving symptoms. Topical corticosteroids (TCS) are the most frequently prescribed class of drugs but long-term therapy is hampered by risks of skin atrophy, dyspigmentation, acneiform eruptions and risks associated with systemic absorption (growth retardation, hypothalamic-pituitary axis effects etc.). Topical calcineurin inhibitors (TCI) are safe and effective short-term treatments but are not suitable for use on severely affected skin. Repeated application of topical therapies over a long period is both time consuming and inconvenient to patients and their families and leads to poor patient adherence with treatment. Patients with moderate to severe AD that is not controlled with optimal topical therapy may require phototherapy or systemic immunosuppressant treatment to achieve adequate disease control. Oral immunosuppressants and glucocorticoids are also effective as short-term or intermittent therapies. However, long-term use is again restricted by concerns over toxicity and side effects. Dupilumab, a monoclonal antibody directed against IL-4 receptor alpha has been recently approved for the treatment of moderate to severe AD in adults by the Food and Drug Administration (Dupixent, 2016), by the European Medicines Agency and Health Canada (Dupixent Product Monograph, 2017/2018).

In inflammatory skin disorders, evidence has accumulated implicating interleukin 17C (IL-17C) as a potential important pro-inflammatory agent. IL-17C expression is induced in cultured keratinocytes by pro-inflammatory cytokines (tumor necrosis factor-alpha [TNFα] and IL-1β) or bacteria (Ramirez-Carrozzi, Sambandam, & Luis, 2011) (Johansen, Riis, & Gedebjerg, 2011). IL-17C itself induces the expression of cytokines, pro-inflammatory mediators, and antimicrobial peptides in epidermal keratinocytes. Increased IL-17C levels were observed in AD subjects leading to an approximately 3-fold upregulation in a one week production rate compared to healthy subjects (Timmis, 2015). In skin biopsies, IL-17C was mainly expressed by the keratinocytes and to some extent in endothelial cells and infiltrating immune cells (Johansen, Riis, & Gedebjerg, 2011) (Johnston, Fritz, & Dawes, 2013). In animal models, intradermal injections of IL-17C, or keratinocytes overexpressing IL-17C, induced skin inflammation or spontaneous psoriatic-like lesions (Ramirez-Carrozzi, Sambandam, & Luis, 2011) (Johnston, Fritz, & Dawes, 2013). In IL-17C or IL-17RE (i.e. IL17C receptor subunit) knock-out mice, the psoriasiform skin inflammation induced by imiquimod, a well-established model, was significantly reduced (Ramirez-Carrozzi, Sambandam, & Luis, 2011).

MOR106 is a purified human recombinant Immunoglobulin G_1 (Ig G_1) monoclonal antibody that binds with a high affinity to human IL-17C, thereby neutralizing its biological activity. It is produced in Chinese Hamster Ovarian cells by recombinant expression technology. MOR106 has significant effects in different rodent inflammatory skin models of AD and psoriasis. Nonclinical safety studies have demonstrated the absence of any adverse effects up to the highest dose tested (see Section 2.1.3) offering beneficial safety margins for Galapagos MOR106-CL-204

047

testing the proposed clinical doses and schedules of this study (see Section 4.2.1). The results of the first-in-human (FIH) Phase 1 study have shown that MOR106 is generally well tolerated in healthy male subjects and subjects with moderate to severe AD, with supportive data from exploratory efficacy assessments in this AD subject group (Timmis, 2015). To date, MOR106 is the first known IL-17C antagonist being evaluated in clinical studies.

This study is being conducted to obtain preliminary safety information on the s.c. administration of MOR106 with concomitant TCS in subjects with moderate to severe AD who are candidates for systemic therapy. Many patients may use MOR106 in combination with TCS. For this reason, it is prudent to assess if MOR106 can be safely co-administered with TCS.

The following paragraphs summarize the results of prior nonclinical (see Section 2.1) and clinical (see Section 2.2) studies for MOR106, more details can be found in the latest investigator's brochure (IB; Edition 3, 29 May 2018).

This clinical study will be conducted in accordance with the current International Council for Harmonisation of Technical Requirements for Pharmaceuticals for Human Use - Good Clinical Practice (ICH-GCP) Guideline E6 (see also Section 10).

2.1. Background - Nonclinical Studies

2.1.1. Nonclinical Pharmacology

2.1.1.1. Primary and Secondary Pharmacology

MOR106 binds with a high apparent affinity to human IL-17C (50% effective concentration $[EC_{50}]$ of 19 ± 6.9 pM). Binding of MOR106 to human IL-17C is approximately 14- to 20-fold stronger compared to binding to cynomolgus monkeys and mice IL-17C, respectively. Binding of MOR106 is specific for IL-17C.

In vitro, MOR106 potently inhibits the binding of human IL-17C to its specific receptor IL-17RE and inhibits the biological activity of IL-17C. MOR106 inhibits the activity of cynomolgus monkeys and mice IL-17C with similar potencies as human IL-17C in contrast to the biochemical binding assay.

MOR106 prevented the occurrence of an AD-like skin inflammation in two different mouse models of AD. MOR106 reduced symptoms of the AD-like syndrome in the MC903 (calcipotriol) mouse model, with a significant impact on epidermal and dermal thickening, inflammation and type 2 T helper cell (Th2)-like gene expression. MOR106 also reduced the development of atopy and overt dermatitis in the skin barrier defective flaky tail model, with effects on gross clinical appearance, acanthosis, mast cell infiltration and serum levels of IgE and Th2-related cytokines IL-4 and thymus and activation regulated chemokine (TARC).

MOR106-CL-204

2.1.1.2. Safety Pharmacology

2.1.2. Nonclinical Pharmacokinetics

2.1.3. Toxicology

Version 4.0, final, 25-Jun-2019

Confidential Information

2.2. Background - Clinical Studies

[figure not shown]
To date, MOR106 has been administered during the single (SAD) and multiple ascending dose (MAD) parts of the FIH Phase 1 study MOR106-CL-101 (Timmis, 2015), as well as in an ongoing Phase 2 study (MOR106-CL-201, 2017) and an ongoing Phase 1 (MOR106-CL-102, 2018).

2.2.1. Clinical Pharmacokinetics and Immunogenicity

2.2.2. Clinical Safety

2.2.3. Clinical Efficacy

3. CLINICAL STUDY OBJECTIVES

3.1. Primary Objective

 To investigate the safety and tolerability of repeated subcutaneous (s.c.) doses of MOR106 administered concomitantly with topical corticosteroids (TCS) in subjects with moderate to severe atopic dermatitis (AD) who are candidates for systemic therapy.

3.2. Secondary Objectives

- To evaluate the PK of repeated s.c. doses of MOR106 administered concomitantly with TCS.
- To monitor the occurrence of anti-drug antibodies (ADA) as a measure of immunogenicity after repeated s.c. doses of MOR106 administered concomitantly with TCS.

3.3. Other Objectives

4. INVESTIGATIONAL PLAN

4.1. Clinical Study Design

This is a randomized, double-blind, placebo-controlled, multicenter Phase 2 study of repeated s.c. doses of 320 mg MOR106 or placebo, administered concomitantly with TCS. On Day 1 a loading dose (LD) will be administered (2 x 320mg MOR106, or placebo).

Adult subjects with moderate to severe AD who are candidates for systemic therapy will be randomized 2:1 to receive MOR106 or placebo every other week via s.c. injections (on Days 1, 15, 29, and 43). The 8-week treatment period, finishing on Day 57, is followed by a 16-week follow-up period, finishing on Day 169. A total of 60 subjects (n=40 on MOR106 and n=20 on placebo) will be enrolled in this study.

The screening visit will take place 7 to 28 days before baseline visit on Day 1. From screening onwards, subjects will apply a bland emollient at least twice daily, for at least 7 days prior to the baseline visit (i.e. Day 1). Emollient use must continue at least twice daily throughout the study (once daily in areas of TCS application).

TCS will not be permitted within 7 days prior to the baseline (Day 1) visit.

From Day 1 onwards, all subjects will apply concomitant open-label, once daily treatment with a medium potency TCS product. Other topical medications, such as a lower potency TCS or topical calcineurin inhibitors (TCI), may be used in addition to treat AD lesions located on the face, flexural, and genital areas. Once control has been achieved (i.e. lesions have cleared or almost cleared), TCS or TCI application to areas from which lesions have cleared will be limited to 2 days every week, in an interval of 3 or 4 days, until the end of the treatment period. TCS or TCI use will be reviewed at every visit by the investigator.

During the 16-week follow-up period, topical treatment of residual active AD lesions may continue as needed at the investigator's discretion.

Eligible subjects will undergo baseline evaluations and randomization, receiving first investigational medicinal product (IMP) dosing on Day 1. Following the completion of the first IMP administration, subjects will remain on site for a minimum of 2 hours after the injections. After the second (i.e. Day 15) and subsequent administrations subjects will remain on site for a minimum of 1 hour after each injection.

[figure not shown]
An interim analysis (after approximately 50% of the subjects having reached the end of treatment period) and a primary analysis (after the end of the treatment period for all subjects) are planned (please refer to Section 7.3.2). At the end of the study the final analysis will be conducted.

For the in- and exclusion criteria please refer to Section 4.5.1, "Inclusion Criteria" and Section 4.5.2, "Exclusion Criteria". A schematic diagram of clinical study design is provided in **Figure 1**.

Version 4.0, final, 25-Jun-2019

Galapagos

MOR106-CL-204

*: TCS use according to approved label.

Figure 1: Schematic overview of the study design.

For detailed info regarding dosage form, packaging and labeling of the IMP please refer to Section 5.2, "Dosage and Administration" and Section 5.3, "Packaging, Labeling and Distribution".

The end of the study is reached when the last follow-up visit or contact as planned according the Schedule of Activities (see Section 6.10) of the last subject is performed.

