4.5.2. Exclusion Criteria

Subjects meeting any of the following exclusion criteria are not eligible for participation in this study:

- 1. Prior treatment with MOR106.
- 2. Known hypersensitivity to any IMP ingredients as determined by the investigator (such as, but not limited to, anaphylaxis requiring hospitalization).
- 3. AD lesions located predominantly (≥50% of the cumulative lesional area) on face and genital areas.
- 4. Having used any of the following treatments:
 - i. Original criterion (CSP Version 3.0, dated 15-Oct-2018):

Prior exposure to a biologic therapy for AD.

i.1 Change of the original criterion (CSP Version 4.0, dated 25-Jun-2019):

Prior exposure to Dupilumab.

- ii. Immunosuppressive/immunomodulating drugs (e.g. systemic corticosteroids, cyclosporine, mycophenolate-mofetil, IFN-γ, azathioprine, methotrexate) within 4 weeks of baseline (Day 1) visit.
- iii. Phototherapy (ultraviolet B [UVB] or Psoralen Ultraviolet A [PUVA]) for AD within four weeks of baseline (Day 1) visit.
- iv. Treatment with TCS or TCI within 7 days before the baseline (Day 1) visit.
- v. Original criterion (CSP Version 3.0, dated 15-Oct-2018):

Treatment with biologics (for non-AD indications) within five half-lives (if known) or 12 weeks prior to baseline visit, whichever is longer.

v.1 Change of the original criterion (CSP Version 4.0, dated 25-Jun-2019):

Treatment with biologics within five half-lives (if known) or 12 weeks prior to baseline visit, whichever is longer.

- vi. Regular use (more than two visits per week) of a tanning booth/parlor within 4 weeks of the baseline visit.
- 5. Original criterion (CSP Version 3.0, dated 15-Oct-2018):

Positive serology for hepatitis B (positive hepatitis B surface [HBs] antigen and/or positive hepatitis core antibody [HBc]) or hepatitis C (anti-HCV) or any history of

MOR106-CL-204

hepatitis from any cause with the exception of hepatitis A. Subjects who are immune to hepatitis B because of vaccination can be included.

5.1 Change of the original criterion (CSP Version 4.0, dated 25-Jun-2019):

Positive serology for hepatitis B (positive hepatitis B surface [HBs] antigen and/or positive hepatitis core antibody [HBc]) or hepatitis C (anti-HCV) or any history of hepatitis from any cause with the exception of hepatitis A and B. Subjects who are immune to hepatitis B because of vaccination can be included.

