4.5.3.2.1. Topical Corticosteroids (TCS)

Subjects will not use any TCS for at least 7 days prior to the baseline (Day 1) visit.

From Day 1 onwards, all subjects will apply concomitant open-label, once daily treatment with TCS as follows:

- Medium potency TCS (e.g. Triamcinolone 0.1% cream or Mometasone furoate 0.1% cream or another sponsor approved TCS) to be used as per approved label.
- Other topical medications, such as a lower potency TCS or TCI, may be used to treat AD lesions located on the face, flexural, and genital areas as per approved label.
- Once control has been achieved (lesions have cleared or almost cleared), TCS or TCI application to areas from which lesions have (almost) cleared, will, under the supervision of the investigator, be limited to twice weekly in intervals of 3-4 days until the end of the treatment period (D57).
- During the follow-up period (D57 to D169), topical treatment of residual active AD lesions may continue as needed at the investigator's discretion. This treatment can be stepped up or stepped down as clinically indicated per investigator's discretion.
- During the follow-up period (D57 to D169), in the event of an AD flare, initiation or escalation of TCS therapy will be recorded as rescue therapy in the follow-up period.

 All TCS (and TCI if used) use will be recorded daily by the subject in a diary from screening visit onwards and throughout the study and will be reviewed at each onsite visit by the investigator.

Detailed instructions on TCS management will be described in a separate study reference manual.

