4.5.3.3. Prohibited Concomitant Medications and Procedures

The following medications are prohibited throughout the study participation:

- Systemic corticosteroids
- Topical tacrolimus and pimecrolimus
- Leukotriene inhibitors
- Allergen immunotherapy
- Systemic treatment for AD with an immunosuppressive / immunomodulating substance (including but not limited to, cyclosporine, mycophenolate-mofetil, azathioprine, methotrexate, biologics or interferon gamma or investigational drugs other than MOR106)
- Treatment with a live (attenuated) vaccine
- Photopheresis, immunoapharesis/-adsorption

The following concomitant procedures are prohibited throughout study participation:

- Elective major surgical procedures
- Concomitant ultraviolet (UV) procedures (phototherapy [narrow band UVB, UVB, UVA1 or PUVA1])
- Tanning in a bed/ booth

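### Protocol Sections 4.1 and 4.5.3.2.1 allow topical calcineurin inhibitors on face, flexural and genital lesions, while Section 4.5.3.3 bans topical tacrolimus and pimecrolimus throughout with no exception

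*Protocol*

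**What the plan says.** **The permission.** Protocol Section 4.1 sets the background regimen from Day 1: a medium potency topical corticosteroid (TCS) once daily, with other topical products as an option, among them "topical calcineurin inhibitors (TCI), may be used in addition to treat AD lesions located on the face, flexural, and genital areas". Section 4.5.3.2.1 says the same of supplementary products, "such as a lower potency TCS or TCI, may be used to treat AD lesions located on the face, flexural, and genital areas", within their approved label. Both sections include TCI in the step-down to two applications a week once lesions clear; 4.5.3.2.1 dates the end of that step-down to Day 57. On monitoring, 4.5.3.2.1 states "All TCS (and TCI if used) use will be recorded daily by the subject in a diary", and 4.1 states "TCS or TCI use will be reviewed at every visit by the investigator".

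**The ban.** Section 4.5.3.3 opens its list with "The following medications are prohibited throughout the study participation". The second item is "Topical tacrolimus and pimecrolimus". No body site, period or cross-reference qualifies it.

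**Related text.** Exclusion criterion 4.iv in Section 4.5.2 rules out "Treatment with TCS or TCI within 7 days before the baseline (Day 1) visit". Section 4.5.3.2.3 allows concomitant medication in general, apart from what 4.5.3.3 prohibits. SAP Section 9.7.4 plans Listing 16.2.4.7, which lists concomitant TCS/TCI records picked out by a dedicated case report form question.

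**The concern.** Tacrolimus and pimecrolimus are the agents a dermatology site would understand by topical TCI, and the protocol names no others. A site that reads 4.5.3.2.1 may apply them to a facial or flexural lesion and record the use in the diary. A site that reads 4.5.3.3 must withhold them. Both would be following the protocol.

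Two things are at stake. The first is uniformity of background treatment on sensitive areas; Section 4.2 gives standardized treatment conditions as the reason for starting TCS together with study drug on Day 1. The second is classification: the same TCI use can be recorded as expected background therapy or as use of a prohibited medication, depending on which section the person coding it relies on.

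**Working it through.** No figure in the plan bears on this point, so the check is textual.

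1. **Do the two rules cover the same products?** The permission is for TCI as a class. The ban names tacrolimus and pimecrolimus. That these are TCIs is drug-class terminology, and the documents do not state it; it is the one step taken from outside them. Nothing in the protocol points to a different TCI that the permission could mean.

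2. **Do they cover the same time?** The permission starts on Day 1 and its explicit schedule ends on Day 57: 57 − 1 = 56 days, the 8-week treatment period. The ban covers all of participation, so the whole of that period falls under both rules. For follow-up, 4.5.3.2.1 speaks only of topical treatment and does not name TCI, although diary recording of any TCI continues. No conflict is claimed there.

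3. **Does eligibility settle it?** No. Criterion 4.iv is a 7-day washout before baseline and treats TCS and TCI alike. TCS is then mandatory from Day 1, so the criterion cannot be read as a continuing ban on either.

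4. **Does the permitted-medications section settle it?** Not fully. The general permission in 4.5.3.2.3 yields to 4.5.3.3, which leans towards the ban. But the TCI permission stands in its own section, 4.5.3.2.1, with sites, label use, step-down and recording, and no text says which of 4.5.3.2.1 and 4.5.3.3 prevails.

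5. **Does an amendment or the SAP settle it?** The Version 4.0 summary of changes concerns exclusion criteria 4 and 5 only. The legible text of SAP Section 8.2.1 says nothing about TCI. Listing 16.2.4.7 suggests that TCI was expected as background therapy, but does not say whether it was allowed.

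6. **Where would a classification error appear?** SAP Section 9.2 tabulates and lists major deviations only. A TCI record would enter Table 14.1.4.1 only if classed as major under the protocol deviation plan, which is not among the documents. The per-protocol set, the one analysis set in the protocol defined by efficacy-relevant deviations, is dropped in SAP Section 8.2.1.

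**The case against.** The strongest reply is that this is a drafting slip with no demonstrated consequence. TCI is optional. Lower potency TCS is open to every site for the same areas. The topical regimen varies by design. Section 4.5.3.2.1 sends detailed TCS instructions to a study reference manual, which may have told all sites the same thing. SAP Section 1.1 also lists a later country-specific protocol for Latvia and Georgia, which is not available here. All of this stands and limits the point, but it does not remove the contradiction from the general protocol: a manual cannot lift a ban that the protocol states.

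A reader might infer more than the documents support:

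- *That TCI users would be counted in the deviation table.* Only major deviations are tabulated, and nothing available shows that label use of TCI on sensitive areas would be classed as major.
- *That a third of the study is affected.* The explicit schedule fills 56 of the 168 days from Day 1 to Day 169 (169 − 1 = 168; 56/168 = 33%), but that is the length of the treatment period. It measures neither TCI exposure nor the number of users.
- *That the arm comparison is biased or an analysis set changes.* Nothing indicates that use would differ by arm, allocation is blinded to the assessing staff, and the full analysis and safety sets do not depend on deviations.

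The direction of the repair is also open to argument, because 4.5.3.2.3 defers to the prohibited list. That is a fair point, and the fix allows for it.

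**Conclusion.** The inconsistency is real in the current Version 4.0 text and does not come from redaction or superseded wording. Two operative treatment rules cannot both be followed, and no available text says which governs. The consequence is possible variation between sites in treating face, flexural and genital lesions, and possible inconsistent handling of the same TCI use as permitted therapy or as a deviation. The number of subjects affected cannot be derived from the documents. No effect on estimates, analysis sets or sample size is claimed. Severity: minor.

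The conclusion rests on tacrolimus and pimecrolimus being TCIs by drug class. The reference manual, the deviation plan and the country-specific protocol were not available; any of them could reduce the practical effect.

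**What to change.** Amend the line in Section 4.5.3.3 to read: "Topical tacrolimus and pimecrolimus", except on face, flexural and genital lesions as allowed in Section 4.5.3.2.1. This direction has the better support: the regimen text gives sites, label use, step-down, diary entry and review; criterion 4.iv treats TCI as a washout item alongside TCS; and SAP Listing 16.2.4.7 provides for concomitant TCI records. Align the protocol deviation plan with the amended line before database lock. A line in that plan alone would not be enough, because it cannot waive a prohibition that the protocol still contains.

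If the sponsor intended the ban, it should instead delete the TCI permission, with the matching step-down wording, from 4.1 and 4.5.3.2.1.

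The SAP introduction reports that development in atopic dermatitis was stopped for futility, so a protocol edit may no longer have any effect. If dosing is over, document which rule governed and classify TCI use the same way at all sites.

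The cost is one protocol line, carried in an amendment with the usual ethics committee submission, and one matching entry in the deviation plan. No new data are needed, since TCS/TCI records are already flagged on the case report form and listed.
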